1. INTRODUCTION

This statistical analysis plan (SAP) describes the rules and conventions to be used in the presentation and analysis of efficacy, safety, pharmacodynamics (PD), pharmacokinetics (PK), and immunogenicity data for Protocol ARGX-113-2211. It describes the data to be summarized and analyzed, including specifics of the statistical analyses to be performed.

The statistical analysis will process and present the results following the ICH standards, in particular the ICH-E3, ICH-E6, and ICH-E9 guidelines^{1,2,3}. This SAP is based on protocol version V1.0, dated 24FEB2023.

2. STUDY OBJECTIVES AND ESTIMANDS

[figure not shown]
Table A : Objectives and Endpoints

Objectives	Endpoints
Primary	

 To evaluate the long-term safety of efgartigimod in patients with pSS 	
 Incidence and severity of adverse event (AEs) and adverse events of Special interest (AESIs), incidence serious adverse events (SAEs), changes in laboratory test results, vital signs, and electrocardiogram (ECG) results
Secondary	

 To evaluate effect and assess long-term effect of efgartigimod on durability of CRESS response 	
 Proportion of Composite of Relevant Endpoints for Sjögren’s Syndrome (CRESS) responders on ≥ 3 of 5 items at weeks 24 and 48 (refer to Section 8.2.1 of the protocol). The 5 items are: 
 Systemic disease activity: clinical EULAR Sjögren’s syndrome disease activity index (clinESSDAI) Patient-reported symptoms: EULAR Sjögren’s Syndrome Patient Reported Index (ESSPRI) Tear gland function: Schirmer’s test and ocular staining score (OSS) Salivary gland function: unstimulated whole salivary flow (UWSF) rate and salivary gland ultrasonography (SGUS) Serology: serum - immunoglobulin G (IgG) and/or rheumatoid factor (RF)

Copyright © 2009, 2010, 2012, 2016, 2018, 2019, 2021, 2024 IQVIA. All rights reserved. The contents of this document are confidential and proprietary to IQVIA Holdings Inc. and its subsidiaries. Unauthorized use, disclosure or reproduction is strictly prohibited.

Objectives	Endpoints

 To evaluate the effect of efgartigimod on clinical efficacy parameters 	
 Proportion of participants with minimal clinically important improvement from baseline in ESSDAI: improvement of ≥ 3 points in ESSDAI score at weeks 24 and 48 Proportion of participants with low disease activity: ESSDAI score of < 5 at weeks 24 and 48 Proportion of participants with minimal clinically important improvement from baseline in clinESSDAI: improvement of ≥ 3 points in clinESSDAI score at weeks 24 and 48 Proportion of participants with low disease activity: clinESSDAI score of < 5 at weeks 24 and 48 Proportion of participants with minimal clinically important improvement from baseline in ESSPRI: decrease of ≥ 1 point or $\geq 15\%$ at weeks 24 and 48 Change from baseline in ESSDAI score at weeks 24 and 48 Change from baseline in clinESSDAI score at weeks 24 and 48 Change from baseline in ESSPRI score at weeks 24 and 48

 To evaluate the effect of efgartigimod on STAR 	
 Proportion of Sjögren’s Tool for Assessing Response (STAR) responders (score of ≥ 5) at weeks 24 and 48 when compared to baseline

 To assess the pharmacodynamics (PD) effect of efgartigimod 	
 Values, changes from baseline, and percent reduction from baseline in total IgG levels in serum over the 48-week treatment period Values, changes from baseline, and percent reduction from baseline in autoantibodies in serum over the 48-week treatment period: 
 Anti-Ro/SS A Anti-La/SS B

 To assess the exposure to efgartigimod 	
 Efgartigimod serum concentrations over the 48-week treatment period

 To assess the immunogenicity of efgartigimod 	
 Incidence and prevalence of antidrug antibody(ies) (ADA) against efgartigimod over the 48-week treatment period
Exploratory	

Copyright © 2009, 2010, 2012, 2016, 2018, 2019, 2021, 2024 IQVIA. All rights reserved. The contents of this document are confidential and proprietary to IQVIA Holdings Inc. and its subsidiaries. Unauthorized use, disclosure or reproduction is strictly prohibited.

Objectives	Endpoints

No estimands have been defined for this study.

3. STUDY DESIGN

3.1. General Description

This is a long-term, single-arm, open-label, multicenter extension of pSS qualifying efgartigimod studies designed to evaluate the long-term safety of efgartigimod in adult patients with pSS. Participants will be enrolled from both active and placebo arms of qualifying efgartigimod studies and receive efgartigimod intravenous (IV) 10 mg/kg over 48 weeks in the extension study without knowledge of their treatment assigned in the qualifying study. To be eligible to enroll in this study, participants must have completed the treatment period of the qualifying study and must not have permanently discontinued the investigational medicinal product (IMP) in that study.

Participants will receive efgartigimod 10 mg/kg by IV infusion either every 2 weeks (Q2W) or once weekly (QW). The dosing regimen is based on whether the participant is a responder or non-responder on day 1. ClinESSDAI assessments to determine responder status using the baseline will be conducted on day 1 and weeks 16 and 24. Responders will receive IV infusions Q2W. Non-responders will receive an infusion QW until such time that they are considered to be responders. If a participant is not a responder at week 24, they will be evaluated by the principal investigator (PI) for therapeutic failure.

- Therapeutic failure - the participant will discontinue study treatment.
- Not a therapeutic failure - the participant will continue QW dosing regimen. ClinESSDAI will be conducted at weeks 32, 36, 40, and 44 until confirming responder status and switching to Q2W dosing regimen. The PI will continue to evaluate the participant for therapeutic failure.

If the participant and/or investigator consider there to be a reduction in therapeutic effect once the patient has switched to Q2W, the participant will return for an unscheduled visit during which a clinESSDAI, a blood sampling for pharmacokinetic (PK) and ADA will be collected.

If there has been an increase in clinESSDAI score of ≥ 3 points and/or a change in score that reclassifies their disease from mild severity to moderate severity the participant will switch to QW dosing regimen and will remain on this dose regimen for the remainder of the treatment period.

Investigational medicinal product (IMP) infusions must occur at the site for a minimum of 3 consecutive visits (for QW dosing regimen: baseline visit and the week 1 and 2 visits; for Q2W dosing regimen: baseline visit and the week 2 and 4 visits) before home infusions are allowed. If doses are missed at 1 or more of these visits, then dosing at subsequent visits will also be on-site. IMP administration at home will not commence until after 3 consecutive doses have been administered on-site.

[figure not shown]
Participants will return for a follow-up visit approximately 56 days after the final IMP administration.

confidential and proprietary to IQVIA Holdings Inc. and its subsidiaries. Unauthorized use, disclosure or reproduction is strictly prohibited.

A minimum of 10 study site visits over the 48-week treatment period and 56-day follow-up period are planned (baseline, weeks 1 [for QW regimen], 2, 4, 8, 12, 16, 24, 36, 48, and the safety follow-up visit (SFV)); all other visits (except for the first 3 consecutive visits) may be conducted by home health care service, or telemedicine visits. The maximum length of time a participant can be in the study is approximately 56 weeks (48 weeks treatment plus 8 weeks of follow-up).

Figure 1: Study Overview

Abbreviations: D = day; IV = intravenous; QW = once weekly; Q2W = every 2 weeks; Wk = week.

^a QW or Q2W dosing regimen depending on responder status. Responders (defined as participants with a decrease in clinESSDAI of ≥ 3 points from baseline of qualifying study or who have a change clinESSDAI score that reclassifies their disease from moderate severity to mild severity) will be switched from QW to Q2W dosing regimen. Non-responders will remain on QW dosing regimen. Switch points (i.e., timepoints where clinESSDAI are conducted to determine responder status) will occur on day 1, week 16, and week 24. If a participant is not a responder at week 24, they will be evaluated by the PI for therapeutic failure. If not considered a therapeutic failure, the participant will continue QW dosing regimen and will return at weeks 32, 36, 40 and 44 for a clinESSDAI assessment until confirming the responder status and switching to Q2W dosing regimen or PI considers the participant to be a therapeutic failure. For QW regimen, the final dose will be administered at week 47. For Q2W regimen, the final dose will be administered at week 46.

3.2. Sample Size

No formal sample size calculation has been planned for this phase 2 open-label extension (OLE) study. Up to approximately 30 subjects who have completed the efgartigimod pSS studies will be enrolled for the OLE study.

3.3. Schedule of Events

Schedule of events can be found in [Section 1.3](#) of the protocol.

3.4. Changes to Analysis from Protocol

The Biomarker data will not be analyzed due to the lack of available data to BIOS.

4. PLANNED ANALYSES

The following analyses will be performed for this study:

- An interim analysis (IA) will be conducted when all subject's complete week 16 or discontinue prior to week 16. If required, more IA will be conducted based on sponsor's discretion.
- Final Analysis

4.1. Data Monitoring Committee (DMC)

There will be no DMC for this study.

4.2. Interim Analysis

One interim analysis will take place after all enrolled subjects of ARGX-112-2211 study complete week 16 or discontinue prior to week 16.

The interim analysis will be performed by IQVIA Biostatistics following authorization of this SAP, database lock, and analysis sets.

Copyright © 2009, 2010, 2012, 2016, 2018, 2019, 2021, 2024 IQVIA. All rights reserved. The contents of this document are confidential and proprietary to IQVIA Holdings Inc. and its subsidiaries. Unauthorized use, disclosure or reproduction is strictly prohibited.

4.3. Final Analysis

All final, planned analyses identified in this SAP will be performed by IQVIA Biostatistics following authorization of this SAP, database lock, and analysis sets.

Pharmacokinetic analysis is being performed by the IQVIA PK group in conjunction with the IQVIA Biostatistics group. PK concentration listings and summary statistics are described in this SAP.

5. ANALYSIS SETS

Agreement and authorization of subjects included/excluded from each analysis set will be conducted prior to database lock.

5.1. Full Analysis Set [FAS]

The full analysis set (FAS) will contain all enrolled subjects in the OLE study.

5.2. Safety Analysis Set [SAF]

The safety analysis set (SAF) will have – All FAS subjects who have been administered study treatment during the OLE.

5.3. PK Analysis Set [PKAS]- efgartigimod

The PK analysis set (PKAS) used for the descriptive summaries of efgartigimod serum concentrations will consist of all enrolled participants who receive at least one dose of efgartigimod and have at least 1 measured concentration of efgartigimod at a scheduled PK time point after start of dosing without protocol violations or events with potential to affect the PK concentration. Participants in this population will be used for all PK summaries.

confidential and proprietary to IQVIA Holdings Inc. and its subsidiaries. Unauthorized use, disclosure or reproduction is strictly prohibited.

6. GENERAL CONSIDERATIONS

6.1. Reference Start Date and Study Day

Study Day will be calculated from the reference start date and will be used to show start/stop day of assessments and events. It will appear in every listing where an assessment date or event date appears.

Reference start date is defined as the day of the first dose of IMP.

- If the date of the event is on or after the reference start date, then:
 - Study Day = (date of event – reference start date) + 1.
- If the date of the event is prior to the reference start date, then:
 - Study Day = (date of event – reference start date).

In the situation where the event date is partial or missing, the date will appear partial or missing in the listings.

Study Day

Date implies a complete date having day, month, and year available. Unless otherwise specified, the study day will remain missing when it cannot be calculated due to absence or incompleteness of the concerned and/or reference dates.

In case the participant never received IMP, the date/time of enrolled will be used instead of first IMP administration date/time.

End of study (EOS) is defined as date of participant's last visit. A participant will have completed the study if the SFV assessments have been completed.

End of treatment (EOT) is defined as date of treatment completion or date of permanent discontinuation of IMP.

6.2. Baseline

Unless otherwise specified, baseline is defined as the last available non-missing measurement from the parent study 2106. Refer to [appendix 1](#) baseline for details. These baseline observations could be either from week 24 or prior visits of ARGX-113-2106. All baseline assessments will be performed before first administration of efgartigimod in ARGX-113-2211, if applicable. The baseline of ECG parameters should come from the same date. If an individual

confidential and proprietary to IQVIA Holdings Inc. and its subsidiaries. Unauthorized use, disclosure or reproduction is strictly prohibited.

ECG parameter is not reported on the latest date prior to 1st IMP infusion within the extension study, leave blank. Assessments do not need to be repeated if they are performed as part of the last visit of the qualifying study. Assessments performed on the same day as the first IMP administration but without time information collected or with time information exactly equal to the time of first IMP administration and which are planned predose will be considered as predose. For parameters related to questionnaires, the baseline is the last value before or at the day of first administration of the IMP, independent of the time of administration. In case the participant never received IMP, the date/time of enrolled will be used instead of first IMP administration date/time. Adverse Events (AEs) and medications commencing on the reference start date will be considered post-baseline unless otherwise indicated based on available start date/time combination or collected electronic case report form (eCRF) information that identifies the individual event/medication as starting prior to first IMP administration.

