2. INTRODUCTION

Participants will be enrolled from both active and placebo arms of qualifying efgartigimod studies in adult patients with pSS. The protocol will be amended to add additional studies at a later date.

In qualifying study ARGX-113-2106, the efficacy and safety of efgartigimod in adult patients with pSS was evaluated using a randomized, double-blinded, placebo-controlled study design. Participants were randomized to receive efgartigimod IV 10 mg/kg or matching placebo in a 2:1 ratio. The IMP (efgartigimod or matching placebo) was administered during the treatment period in approximately 1-hour IV infusion QW by site or a home nurse. The final dose was administered at week 23. At week 24, eligible participants from ARGX-113-2106 may roll over into the present single-arm OLE study: ARGX-113-2211.

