3. OBJECTIVES, ENDPOINTS, AND ESTIMANDS

Table 2: Study ARGX-113-2211 Objectives and Endpoints

Objectives	Endpoints
Primary	

 To evaluate the long-term safety of efgartigimod in patients with pSS 	
 Incidence and severity of AEs and AESIs, incidence SAEs, changes in laboratory test results, vital signs, and ECG results
Secondary	

 To evaluate effect and assess long-term data on durability of CRESS response 	
 Proportion of CRESS responders on ≥ 3 of 5 items at weeks 24 and 48 (refer to Section 8.2.1). The 5 items are: 
 Systemic disease activity: clinESSDAI Patient-reported symptoms: ESSPRI Tear gland function: Schirmer’s test and OSS Salivary gland function: UWSF rate and SGUS Serology: serum IgG and/or RF

 To evaluate the effect of efgartigimod on clinical efficacy parameters 	
 Proportion of participants with minimal clinically important improvement from baseline in ESSDAI: improvement of ≥ 3 points in ESSDAI score at weeks 24 and 48 Proportion of participants with low disease activity: ESSDAI score of < 5 at weeks 24 and 48 Proportion of participants with minimal clinically important improvement from baseline in clinESSDAI: improvement of ≥ 3 points in clinESSDAI score at weeks 24 and 48 Proportion of participants with low disease activity: clinESSDAI score of < 5 at weeks 24 and 48 Proportion of participants with minimal clinically important improvement from baseline in ESSPRI: decrease of ≥ 1 point or $\geq 15\%$ at weeks 24 and 48 Change from baseline in ESSDAI score at weeks 24 and 48 Change from baseline in clinESSDAI score at weeks 24 and 48 Change from baseline in ESSPRI score at weeks 24 and 48

 To evaluate the effect of efgartigimod on STAR 	
 Proportion of STAR responders (score of ≥ 5) at weeks 24 and 48 when compared to baseline

Objectives	Endpoints

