
 To assess the PD effect of efgartigimod 	
 Values, changes from baseline, and percent reduction from baseline in total IgG levels in serum over the 48-week treatment period Values, changes from baseline, and percent reduction from baseline in autoantibodies in serum over the 48-week treatment period: 
 Anti-Ro/SS A Anti-La/SS B

 To assess the exposure to efgartigimod 	
 Efgartigimod serum concentrations over the 48-week treatment period

 To assess the immunogenicity of efgartigimod 	
 Incidence and prevalence of ADA against efgartigimod over the 48-week treatment period
Exploratory	

 To explore the effect of efgartigimod on additional clinical pSS measures 	
 Proportion of responders on 2 of 4 items of the adjusted CRESS (without serology item) at weeks 24 and 48 when compared to baseline Change from baseline in activity of individual ESSDAI domains at weeks 24 and 48

 To explore the effect of efgartigimod on glandular measures 	
 Change from baseline in: 
 SWSF rate at weeks 24 and 48 UWSF rate at weeks 24 and 48 Hocevar score at weeks 24 and 48 Schirmer's test at weeks 24 and 48 OSS at weeks 24 and 48 Response in salivary gland as defined in CRESS at weeks 24 and 48 when compared to baseline Response in tear gland as defined in CRESS at weeks 24 and 48 when compared to baseline

 To explore the effect of efgartigimod on patient-reported outcomes 	
 Change from baseline in: 
 Total MFI score at weeks 24 and 48 Physical component and mental component scores of SF-36 at weeks 24 and 48 PGA at weeks 24 and 48 Individual ESSPRI scores at weeks 24 and 48 EQ-5D-5L utilities and VAS scores at weeks 24 and 48 PASS at weeks 24 and 48 when compared to baseline

Objectives	Endpoints

 • CCI [REDACTED] 	
 • CCI [REDACTED] • Values, changes from baseline, and percent reduction from baseline in RF in serum over the 48-week treatment period

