9.3. Statistical Analyses

9.3.1. General Considerations

- Data collected will be listed with derived variables. Descriptive statistical methods will be used to analyze safety and efficacy data
- The results of this study will not be used inferentially
- No formal sample size calculation is presented
- Summaries will include the number of observations (n), mean, SE, 90% CI, median, minimum, and maximum for continuous measures
- Summaries will include sample size, frequencies, and percentages for categorical variables
- The baseline value will be the last assessment before the first administration of the study drug in OLE
- All study visits will be recalculated based on actual dates. The rules for calculating the analysis visits will be documented in the SAP
- Rules for imputing partial dates or missing dates will be provided in the SAP
- Exposure to IMP will be summarized
- TEAEs, AESIs, SAEs, and other safety parameters will be summarized
- AEs will be classified using the latest version of the MedDRA classification system
- AEs, AESIs, and SAEs will be listed corresponding to MedDRA SOC and PT

- Multiple occurrences of a single PT in a participant will be counted only once at the maximum severity/grade
- AEs with missing severity or relationship to IMP will be classified as severe and treatment-related, respectively. All AEs will be summarized by relatedness to IMP
- Any AEs leading to death or discontinuation of IMP will also be summarized
- Population PK/PD analysis may be performed based on the PK and PD data and reported separately
- Laboratory parameters, physical examinations, vital sign measurements, ECG data and PK, PD, immunogenicity, and biomarker results will be summarized descriptively

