For the reporting of descriptive statistics for PK data, the mean and SD will be presented to one digit more precision than the source data except values ≥ 1000 which will be presented without the decimals and rounded to the nearest integer. The minimum, median, and maximum will be presented to the same precision as the source data. Coefficient of variation will always be reported to 1 decimal place. Individual serum concentrations will be reported as received by the bioanalytical laboratory.

Descriptive statistics for immunogenicity titer values will include the number of observed values, arithmetic mean, SE, 90% CI, median, Q1, Q3, minimum, maximum, the geometric mean, and geometric CV%.

For event-type safety data, the number and percentage of participants with an event will be shown. The denominator will be all participants in the analysis set.

For frequency tabulations and cross-tabulations, the denominator will be the number of participants. For tables where results are shown by analysis visit, the denominator will be the number of participants and analysis visit.

Missing values will not be included in the denominator count when computing percentages. For cross-tabulation of post-baseline results versus baseline results, a “missing” category will be shown for baseline results, if applicable. Percentages will be presented with 1 decimal place.

Summaries will be provided both for the overall study population as well as grouped according to treatment received in the parent study AGRX-113-2106 (efgartigimod or placebo). [Appendix 1](#) shows conventions for presentation of data in outputs.

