Plots of mean changes from the OLE baseline will be presented along with their 90% confidence intervals at each scheduled timepoint of week 16, 24, 36 and 48 for ESSDAI, clinESSDAI, and ESSPRI. Box and Whisker plots will also be presented for the change from OLE baseline for each scheduled timepoint.

Copyright © 2009, 2010, 2012, 2016, 2018, 2019, 2021, 2024 IQVIA. All rights reserved. The contents of this document are confidential and proprietary to IQVIA Holdings Inc. and its subsidiaries. Unauthorized use, disclosure or reproduction is strictly prohibited.

13.1.6. Proportion of Participants with STAR Score of ≥ 5 at Week 24 and 48

STAR has been developed to assess the efficacy of treatments for pSS.

The details of each of the components remains the same as explained in Section 14.2.1.1. This composite measure contains 5 domains (like CRESS):

- Systemic activity: If participant has clinESSDAI score decreased by ≥ 3 points at week 24 and 48, in that case the participant will be scored with 3 points.
- Patient-reported outcome: If participant has ESSPRI score decrease of at least 1 point or $\geq 15\%$ at week 24 and 48, in that case the participant will be scored with 3 points.
- Lacrimal gland function (assessed by Schirmer's test or OSS)

Here there are two criteria associated w.r.t Schirmer's test:

- If Schirmer's test is ≤ 5 mm at baseline (abnormal) in at least 1 eye, a response is defined as an increase of at least 5 mm from baseline.
- If Schirmer's scores are normal in both eyes at baseline, a response is defined as no change to abnormal.

Also, there are two criteria associated w.r.t OSS:

- If OSS score ≥ 3 points at baseline (abnormal) in at least 1 eye, a response is defined as a decrease of at least 2 points from baseline.
- If OSS scores are normal in both eyes at baseline, a response is defined as no change to abnormal.

If either of the Schirmer's test or OSS assessment criteria are met, 1 point is assigned.

- Salivary gland function

Here there are two criteria associated w.r.t UWSF:

- If score > 0 at baseline: increase of $\geq 25\%$ from baseline.
- If score is 0 at baseline: any increase in UWSF from baseline.

OR

SGUS: $\geq 25\%$ decrease in total Hocevar score from baseline

[figure not shown]
[figure not shown]
If either of the UWSF or SGUS assessment criteria are met, 1 point is assigned.

- Biological (assessed by IgG or RF): 1 point is assigned if,
 - IgG: $\geq 10\%$ reduction
 - RF: $\geq 25\%$ decrease

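### For participants who already received efgartigimod, CRESS, STAR and minimal-improvement response are measured from an on-treatment baseline, so a fully maintained response counts as nonresponse

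*SAP*

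**What the plan says.** SAP 6.2 sets the general rule: "baseline is defined as the last available non-missing measurement from the parent study 2106". It allows the value to come from parent week 24 or an earlier visit, and the footnote to SAP Table C repeats the rule for clinESSDAI. Protocol 9.3.1 reaches the same point from the other side: "The baseline value will be the last assessment before the first administration of the study drug in OLE".

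Protocol section 2 gives the timing in the parent study. Participants were randomised 2:1 to weekly efgartigimod or placebo, and "The final dose was administered at week 23", with rollover at week 24.

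The CRESS endpoint sits under the first secondary objective, worded in the protocol as "To evaluate effect and assess long-term data on durability of CRESS response" and in the SAP as "long-term effect of efgartigimod on durability of CRESS response". Protocol 4.3 adds that the Q2W regimen was chosen for responders to see whether less frequent dosing keeps efficacy.

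SAP 13.1.1 to 13.1.4 and 13.1.6 define CRESS, STAR and the ESSDAI, clinESSDAI and ESSPRI improvement rates, with no separate reference for any of them. For change scores SAP 13.1.5 is explicit: "Plots of mean changes from the OLE baseline will be presented". SAP 7.2 presents results overall and also "grouped according to treatment received in the parent study".

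**The concern.** For former placebo participants, OLE entry precedes any efgartigimod, so response measured from there is new response. For former efgartigimod participants it comes about one week after the last of the weekly parent doses, so any benefit is already in the reference value. Most of the responder criteria require change from that value. Measured this way, the endpoint asks whether a participant improved further on treatment, not whether the response lasted.

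Two things are at stake. A low CRESS or STAR proportion in the former efgartigimod arm could be read as loss of efficacy when nothing was lost. The overall column would also blend two quantities: further improvement in one group and first response in the other. The same blend affects pooled percent change in IgG.

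**Working it through.** The plan has no sample-size calculation or assumed response rate to reproduce. The check is to score, under the written rules, a participant whose values do not change from OLE entry.

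**Inputs.** CRESS rules: protocol 8.2.1 and SAP 13.1.1. STAR rules: protocol 8.2.4 and SAP 13.1.6. Minimal-improvement rules: protocol Table 2. Domain weights: protocol Table 5. Size: up to about 30 (protocol 9.5). Parent ratio: 2:1 (protocol section 2). IgG reduction on weekly dosing: 60% to 70%, from other indications and modelling (protocol 4.3).

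**Score at zero change** (a percent change from a zero baseline is undefined and taken as not met):

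| Component | CRESS | STAR |
|---|---|---|
| Systemic | Can be met (clinESSDAI < 5, no baseline needed) | 0 of 3 (needs a fall of ≥ 3) |
| ESSPRI | Not met | 0 of 3 |
| Tear/lacrimal | Can be met if Schirmer and OSS are both normal at entry | 1 of 1 if either test is normal at entry |
| Salivary | Not met | 0 of 1 |
| Serology | Not met | 0 of 1 |
| Maximum | 2 of 5 (3 needed) | 1 of 9 (5 needed) |

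All 8 combinations of clinESSDAI < 5, Schirmer normal and OSS normal (each yes/no) give these maxima, and so does a wider grid of entry values. No ESSDAI, clinESSDAI or ESSPRI minimal-improvement endpoint is met in any state.

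**Example (assumed values).** From parent pre-treatment to week 24: clinESSDAI 12 to 3, ESSPRI 7 to 5, Schirmer 3 to 9 mm, OSS 6 to 2, UWSF 0.10 to 0.15 mL/min, Hocevar 28 to 20, IgG down 65%, RF 60 to 30. Against the pre-treatment baseline this is CRESS 5/5 and STAR 9/9. If the same state is held through the OLE, it scores CRESS 2/5 and STAR 1/9 against OLE entry.

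**Effect on proportions.** Each such participant costs 1/30 = 3.3 points pooled, or 1/20 = 5.0 points in the former efgartigimod arm (20:10 split assumed). Suppose all 20 hold their week-24 state and 8, 12 or 16 of them were responders against the pre-treatment baseline:

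| Maintained responders | Pre-treatment baseline (exact 90% CI) | Planned baseline |
|---|---|---|
| 8/20 | 40% (21.7 to 60.6) | 0/20 (0 to 13.9) |
| 12/20 | 60% (39.4 to 78.3) | 0/20 (0 to 13.9) |
| 16/20 | 80% (59.9 to 92.9) | 0/20 (0 to 13.9) |

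The planned pooled rate then cannot exceed 10/30 = 33.3%, even if every former placebo participant responds.

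**Floor.** With the Table 5 weights, possible clinESSDAI totals begin 0, 2, 3, 4, 5. Someone entering at 0 or 2 can never show a 3-point fall or earn the 3 STAR systemic points. The same floor applies to ESSDAI 0 to 2.

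**IgG.** If IgG is already 60% to 70% down at entry (assumed to hold in pSS), a further 10% fall needs total suppression of 1 − 0.9 × 0.40 = 64% to 1 − 0.9 × 0.30 = 73%. If everyone then sits at an unchanged 60% to 70%, the former efgartigimod arm contributes zero change. The pooled mean fall is placebo share × suppression:

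- share 1/3: 20% to 23%
- share 25% to 40% (assumed): 0.25 × 60% = 15% to 0.40 × 70% = 28%

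If suppression instead eases from 65% to 50% (assumed), the former efgartigimod arm reads 0.50/0.35 − 1 = +43% against OLE entry but −50% against pre-treatment. The pooled mean is 2/3 × 43% − 1/3 × 50% = about +12%.

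**The case against.** The SAP follows the protocol's own baseline in a descriptive study whose primary objective is safety. Every summary is also shown by parent arm, actual scores are tabulated, and the ESSDAI < 5 and clinESSDAI < 5 rates need no baseline and can describe a maintained state. The objective covers effect as well as durability, and for former placebo participants the planned endpoint serves both. SAP 6.2 allows exceptions and refers to Appendix 1, which is not in the available text. SAP 13.2 and 13.3 are redacted, so another reference could be defined in either place.

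Part of this stands. The problem is confined to the former efgartigimod arm. It does not reach the < 5 endpoints, change scores read by parent arm, or the exploratory adjusted CRESS (2 of 4), which can be met at zero change. Real participants fluctuate or improve further, including through a further 25% fall in RF, so observed rates need not be zero. The clinESSDAI floor applies to either arm. The IgG figures are scenarios only: 60% to 70% comes from weekly dosing, responders receive Q2W, and the sign of the pooled mean can reverse.

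The main point is not answered. Splitting by arm leaves the reference within the former efgartigimod arm unchanged, each < 5 rate covers one instrument rather than CRESS, and protocol 9.3.1 fixes the OLE-entry baseline independently of Appendix 1.

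**Conclusion.** The concern holds and should be fixed. For the former efgartigimod arm, the planned CRESS, STAR and minimal-improvement proportions measure further improvement on treatment. They cannot show that a response was kept, because exact maintenance always scores as nonresponse. Pooled proportions and pooled IgG change mix two quantities. The scoring maxima follow from the rules alone. The per-participant figures assume 30 participants, 2:1 carry-over and complete data; because efficacy uses observed data, missing values would shrink the denominators.

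Immunogenicity needs a related caution. ADA already present at OLE entry counts towards incidence only if boosted, although prevalence and the baseline-positive tables can show it.

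Separately, the documents conflict on the reference for dosing-responder status. The protocol synopsis and schema, and the SAP study-overview figure, use the baseline of the qualifying study. Protocol 4.1 explains baseline as that study's final visit. The schedule of activities makes that visit the OLE baseline, so under 4.1 the day-1 change would be zero by construction. These passages must be reconciled.

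**What to change.** - In SAP 13.1.1 to 13.1.4 and 13.1.6, add CRESS, STAR and minimal-improvement response at OLE weeks 24 and 48 by parent arm. Reference former efgartigimod participants to their parent pre-treatment baseline, and former placebo participants to the last value before the first OLE dose.
- As the analysis that addresses durability, report the share of parent week-24 CRESS responders in the efgartigimod arm who still respond at OLE weeks 24 and 48, with exact 90% CI.
- In SAP 14, also show percent change in IgG and autoantibodies for the former efgartigimod arm against the parent pre-treatment baseline.
- Keep the protocol's OLE-baseline results but interpret them by parent arm. Do not pool the added results: at OLE week 24 the groups have had about 48 and 24 weeks on drug.
- Declare the additions in SAP 3.4.

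The cost is programming, tables and the SAP note, with no new visits or assessments. This assumes that the parent pre-treatment component values and week-24 CRESS status are available in compatible form. The SAP already draws on parent-study values and parent arm. The durability estimate will be imprecise: if 80% of an assumed 10 or 15 parent responders persist, the exact 90% CI is 49% to 96% (8/10) or 56% to 94% (12/15).
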